8.1.5 Visit 20 *or Visit 22 (if applicable)*

2.10 Protocol, Section 8.5.2 Laboratory assessments for safety, page 38

For laboratory analysis of safety parameters, the volumes of blood sampling at each visit are as follows:

- At Visit 1 (screening), Visit 8, Visit 12, Visit 16 ~~and~~ *Visit 20 and Visit 22 (if applicable)*, 14.1 mL of blood will be drawn for each visit.
- At Visit 3, Visit 5, Visit 7, Visit 9, Visit 11 ~~Visit 13, Visit 15, Visit 17 and~~ *Visit 19 and Visit 21 (if applicable)*, 5.5 mL of blood will be drawn for each visit.
- At Visit 6, Visit 10, Visit 14 and Visit 18, 7.8 mL of blood will be drawn.

2.11 Protocol, Section 8.5.2.1 Haematology, page 39

At Visits 1, 3, 5, 6, 7, 8, 9, 10, 11, 12, 13, 14, 15, 16, 17, 18, 19 and 20, *and Visits 21 and 22 (if applicable)*, blood samples will be drawn for the measurement of the following:

2.12 Protocol, Section 8.5.2.2 Biochemistry, page 40

At Visits 1, 3, 5, 6, 7, 8, 9, 10, 11, 12, 13, 14, 15, 16, 17, 18, 19 and 20, *and Visits 21 and 22 (if applicable)*, blood samples will be drawn for the measurement of the following:

2.13 Protocol, Section 8.5.2.3 Bone metabolism marker, page 40

At Visits 1, 6, 8, 10, 12, 14, 16, 18, and 20, *and Visit 22 (if applicable)*, blood samples will be drawn for the measurement of the following:

2.14 Protocol, Section 8.5.2.4 Lipid, page 40

At Visits 1, 3, 5, 6, 7, 8, 9, 10, 11, 12, 13, 14, 15, 16, 17, 18, 19 and 20 ~~the final visit~~, *and Visits 21 and 22 (if applicable)*, blood samples will be drawn for the measurement of the following:

2.15 Protocol, Section 8.5.2.5 Endocrinology, page 41

At Visits 1, 3, 5, 6, 7, 8, 9, 10, 11, 12, 13, 14, 15, 16, 17, 18, 19 and 20, *and Visits 21 and 22 (if applicable)*, blood samples will be drawn for the measurement of the following:

2.16 Protocol, Section 8.5.2.6 IGF-I, page 41

At Visits 1, 3, 5, 6, 7, 8, 9, 10, 11, 12, 13, 14, 15, 16, 17, 18, 19 and 20, *and Visits 21 and 22 (if applicable)*, blood samples will be drawn for the measurement of IGF-I.

2.17 Protocol, Section 8.5.2.7 Blood coagulation tests, page 41

At Visits 1, 6, 8, 10, 12, 14, 16, 18 and 20, *and Visit 22 (if applicable)*, blood samples will be drawn for the measurement of the following:

2.18 Protocol, Section 8.5.2.8 Urine samples, page 41

At Visits 1, 3, 5, 6, 7, 8, 9, 10, 11, 12, 13, 14, 15, 16, 17, 18, 19 and 20, *and Visits 21 and 22 (if applicable)*, urine samples will be drawn for the measurement of the following:

2.19 Protocol, Section 8.5.2.9 OGTT, page 41

The OGTT will be performed at Visit 1, 8, 12, 16 and 20, *and Visit 22 (if applicable)*. At Visit 1, the OGTT will be performed between Visit 1 and ending the time the subjects are registered (just before Visit 2). At Visits 8, 12, 16 and 20, *and Visit 22 (if applicable)*, the OGTT will be performed within the visit window stated in the flow chart (section 2). After having fasted apart from water from 9 pm in the previous night, the OGTT will be conducted.

2.20 Protocol, Section 8.5.2.10 HbA_{1c}, page 42

At Visits 1, 6, 8, 10, 12, 14, 16, 18, and 20, *and Visit 22 (if applicable)*, blood samples will be drawn for the measurement of HbA_{1c}.

2.21 Protocol, Section 8.5.4 ECG, page 42

A 12-lead ECG will be recorded after a 3-minute rest in a supine position at Visits 1, 6, 8, 10, 12, 14, 16, 18 and 20, *and Visit 22 (if applicable)*. At Visit 1, the 12-lead ECG will be recorded between Visit 1 and ending the time the subjects are registered (just before Visit 2). At Visits 6, 8, 10, 12, 14, 16, 18 and 20, *and Visit 22 (if applicable)*, the 12-lead ECG will be recorded within the visit window stated in the flow chart (section 2). The ECG reader will compute the PR, QT and QTc intervals (QT intervals corrected for heart rate), QRS duration, and RR interval and heart rate. The PR, QT and QTc intervals, QRS duration, and RR interval and heart rate will be recorded in the CRF.

2.22 Protocol, Section 8.5.5 Transthoracic echocardiography, page 43

A transthoracic echocardiography (TTE) will be performed at Visits 1, 6, 8, 10, 12, 14, 16, 18 and 20, *and Visit 22 (if applicable)*. At Visit 1, the TTE will be performed between Visit 1 and ending the time the subjects are registered (just before Visit 2). At Visits 6, 8, 10, 12, 14, 16, 18 and 20, *and Visit 22 (if applicable)*, the TTE will be performed within the visit window stated in the flow chart (section 2).

2.23 Protocol, Section 8.6.3 Genetic test, page 44

8.6.3 Genetic test

Noonan syndrome is diagnosed by clinical diagnosis score list. The gene mutations that cause to become Noonan syndrome are found in approximately 70% of the patients but not all patients. Therefore, genetic test will be performed for subjects participating in this trial and intending to take the test.

Gene responsible for Noonan syndrome can be tested during the extension phase.

If the subject's parent or the subject's legally acceptable representative wants a genetic test of a gene responsible for Noonan syndrome for her/his child, an informed consent form should be obtained from the subject's parent or the subject's legally acceptable representative. If the subject has the ability to understand (as per the investigator's discretion), an assent form should be obtained from that subject.

The PTPN11, KRAS, SOS1, RAF1, BRAF, SHOC2, NRAS or RIT1 may be identified as the gene responsible for Noonan syndrome by the genetic test. The results are only to be used for statistical analysis. The blood samples are discarded appropriately after the genetic tests.

The genetic tests will be performed by a specific laboratory.

Collection and sending of the samples will be performed by the central laboratory as for other samples. Laboratory supplies and procedures for obtaining samples, handling and storage of samples and information on who will perform the assessments, will be described in a trial-specific laboratory manual provided by the central laboratory.

2.24 Protocol, Section 10 Interactive voice/web response system, page 48

Table 5-1 Trial design of this trial

Trial GHLIQUID-4020	Extension phase									
								End of Treatment ^{a)}		End of Treatment
Visit (V)	V13	V14	V15	V16	V17	V18	V19	V20	V21	V22
Time of visit (weeks)	117	130	143	156	169	182	195	208	221	234
Visit window (days)	±14	±14	±14	±14	±14	±14	±14	±14	±14	±14
Screening										
Screening failure										
Randomisation										
Dispensing	X	X	X	X	X	X	X	X ^{b)}	X	
Data change	(X)	(X)	(X)	(X)	(X)	(X)	(X)	(X)	(X)	(X)
Withdrawal	(X)	(X)	(X)	(X)	(X)	(X)	(X)	(X) ^{b)}	(X)	
Completion								X ^{c)}		X
Drug accountability	X	X	X	X	X	X	X	X	X	X

^{a)} The extension phase can be further extended for 26 weeks for subjects who will complete visit 20 no later than the end of the month following marketing approval date for use of Norditropin for treatment of 'short stature due to Noonan syndrome' who consent to receive the trial products during the period. For subjects who will receive trial treatment for further 26 weeks, visits 21 and 22 should be conducted.

^{b)} For subjects who will complete the trial treatment at week 208, the assessment will not be performed at visit 20. For subjects who will receive trial treatment for further 26 weeks, the assessment should be performed at visit 20.

^{c)} For subjects who will complete the trial treatment at week 208, the end of trial form should be completed at visit 20. For subjects who will receive trial treatment for further 26 weeks, the end of trial form should be completed at visit 22.

2.25 Protocol, Section 12.2 Reporting of adverse events, page 55

All events meeting the definition of an AE must be collected and reported. This includes events from the first trial-related activity after the subject's parent or the subject's legally acceptable representative has signed the informed consent until the completion of procedures at Visit 20 or Visit 22 (if applicable). The events must be recorded in the applicable forms in a timely manner.

2.26 Protocol, Section 17.4.3 Endpoints for the whole trial including the extension phase, page 70

The period of the extension phase is 104 weeks, and the period of the whole trial will be 208 weeks [104 weeks in the pivotal phase and 104 weeks in the extension phase]. However, ~~if the indication has not yet been approved or rejected by the PMDA at 208 weeks for the first subject, the period for the extension phase will be extended for at least 26 weeks (6 months)~~ the extension phase can be further extended for 26 weeks (to week 234) for subjects who will complete visit 20 (week 208) no

later than the end of the month following marketing approval date for use of Norditropin for treatment of ‘short stature due to Noonan syndrome’ who consent to receive the trial products during the period.

The endpoints at 208 weeks for the whole trial including the extension phase are defined in the same way as for the pivotal phase. *Data collected in the further extended extension phase will only be summarised descriptively.*

All efficacy and safety endpoints and parameters *after 208 weeks of treatment* will be summarised and analysed in the same way as for the 104 weeks.

2.27 SIIC, Section 1.2 What is a clinical?, page 4

This trial will be classified as post marketing clinical trial after getting marketing approval for treatment of ‘short stature due to Noonan syndrome’ in Japan, and then the term “clinical trial” will be replaced with “post marketing clinical trial”. Other implementation is not changed.

2.28 SIIC, Section 1.5 Treatment in this trial, page 4

You will be provided with NN-220 on Visit 2, and please subcutaneously inject it once a day from that day until the previous night of Visit 20 *or* Visit 22.

2.29 SIIC, Section 1.6 Trial period, page 5

The trial period of this trial is 208 weeks. However, ~~if the indication has not been approved by PMDA at 208 weeks for the first subject, the period for the extension phase will be extended. You will be explained before 208 weeks for the first subject whether the period for the extension phase will be extended or not~~ *if the 208 week-treatment is completed by the end of next month of marketing approval date, 26 weeks can be extended for the treatment period (Visit 21 and Visit 22 are added in case of extending the period).* In case NN-220 is not approved as a “Medicine”, specifically, when this developmental program is terminated or if the MHLW rejects the marketing application, this trial will be stopped and the treatment for your child with NN-220 will be ended.

Please continue the treatment until the previous night of Visit 20 *or* Visit 22. At Visit 20 *or* Visit 22, the trial will be completed.

If your child participates in this trial, the number of visiting the hospital/clinic is 20 *or* 22. If your trial doctor needs your child to visit the hospital/clinic at short intervals, more visits may be requested.

2.30 SIIC, Section 1.7.2 Trial schedule, page 6

[figure not shown]

Figure 1-1 Trial diagram (updated figure is presented)

2.31 SIIC, Section 1.7.2 Trial schedule, page 8

Table 1-1 Trial schedule

Item \ Period (weeks)	Visit 13	Visit 14	Visit 15	Visit 16	Visit 17	Visit 18	Visit 19	Visit 20	Visit 21 ^{*2}	Visit 22 ^{*2}
	Time (weeks) from Visit 2									
	117	130	143	156	169	182	195	208	221	234
Need to be fasting				○				○		○
Medical examination/interview ^{*1} , measurement of height, body weight, blood pressure, and pulse	○	○	○	○	○	○	○	○	○	○
Electrocardiogram (ECG)		○		○		○		○		○

1.1 Trial information

This is a multicentre, randomised, parallel-group double-blind trial investigating the long-term efficacy and safety of two doses of NN-220 in short stature due to Noonan syndrome. Primary objective is to evaluate the growth promoting effect of NN-220 from baseline to 104 weeks of treatment in short stature due to Noonan syndrome. Refer to the protocol for further details.

1.2 Scope of the statistical analysis plan

This Statistical Analysis Plan (SAP) is based on the statistical analyses of GHLIQUID-4020 as planned in the trial protocol.

Changes to the statistical methods proposed in this SAP and the reason for the change must be reported in the clinical trial report (CTR).

This SAP is based on the protocol version 2.0 (Dated 03 March 2016).

2 Statistical considerations

Analyses of all efficacy endpoints will be performed based on the full analysis set (FAS). The primary analysis of the primary endpoint will be repeated on the per protocol (PP) analysis set.

Safety endpoints will be summarised using the safety analysis set (SAS).

The impact of protocol deviations and outliers may be investigated further in sensitivity analyses if deemed relevant.

Missing values for endpoints other than OGTT, HbA_{1c} and bone age will be imputed using the last observation carried forward (LOCF) method.

All endpoints will be summarised descriptively at each visit by treatment using observed data. After 104 weeks of treatment, descriptive statistics will be presented based on both observed and LOCF imputed data. Endpoints that are analysed untransformed and endpoints that are not formally analysed are summarised by the arithmetic mean, standard deviation (SD), median, and minimum and maximum value. Endpoints that are analysed log-transformed are summarised by the geometric mean, coefficient of variation (CV), median, minimum and maximum value.

LOCF imputed data will be used as the basis for plotting data.

A formal statistical test will only be performed at 104 weeks. Presentation of results from a statistical analysis will include the estimated mean treatment effects (LSMeans). Estimated mean

treatment differences (or ratios) will be presented together with two-sided 95% confidence intervals and p values for all endpoints analysed statistically.

For endpoints measured over time mean values will be plotted to explore the trajectory over time. Data collected before randomisation will only be summarised descriptively.

Statistical analysis will be performed twice, at 104 weeks and at the end of trial including extension phase.

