6.1 Number of subjects

Country planned to participate: Japan

Number of sites planned to participate: 34

Number of subjects planned to be screened (i.e., documented informed consent): 53

Number of subjects planned to be randomised: 48

0.033 mg/kg/day group: 24

0.066 mg/kg/day group: 24

Number of subjects expected to complete the trial: 42

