8.1.4.3 Withdrawn subjects

Subjects randomised in error must be withdrawn from the trial.

If a subject is withdrawn from the trial,

- the investigator must aim to undertake procedures similar to those for Visit 20 as soon as possible.

- although a subject is not obliged to give his/her reasons for withdrawing from the trial, the investigator should make a reasonable effort to ascertain the reason, while fully respecting the subject's rights. Where the reasons are obtained, the primary reason (AE, non-compliance with the protocol, withdrawal criteria or others) for discontinuation must be specified in the CRF.
- a withdrawal session must be performed using the IV/WRS.
- the end of trial form must be completed, and final drug accountability of trial products must be performed even if the subject is not able to come to the site.

8.1.5 Visit 20

Please see flow chart (section [2](#)) and assessment sections (sections [8.2](#), [8.3](#), [8.4](#), [8.5](#) and [8.6](#))

The subjects must attend fasting, having consumed only water from 9 pm the previous evening.

Subjects will be asked to bring all empty, partly used and unused trial products for drug accountability of trial products.

Drug accountability should be performed using the IV/WRS drug accountability module to confirm allocated, returned and lost pen devices.

The subject completion should be registered in the IV/WRS by performing a completion session.

The investigator will complete an end of trial form.

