17.1 Sample size calculation

The primary endpoint is change in height SDS from baseline to 104 weeks of treatment¹⁷. Since the primary objective of this trial is to evaluate the growth promoting effect of NN-220, the following hypothesis will be statistically tested; $H_0: \mu_1 = \mu_2$ vs. $H_1: \mu_1 \neq \mu_2$, where μ_i is the population mean, i

=1, 2 represents the 0.033 mg/kg/day and 0.066 mg/kg/day, respectively. Primary analysis for primary endpoint will be performed based on the analysis of covariance (ANCOVA) model with treatment as a fixed effect and baseline height SDS as a covariate.

The sample size is calculated using two sided two sample t-test for $\mu_1 = \mu_2$ with a 5% significance level.

According to Osio D., et al. (2005)⁷, the mean (SD) of change in height SDS of treatment with 0.033 mg/kg/day and 0.066 mg/kg/day from baseline was 0.8 (0.4) after 1 year and a further mean gain of 0.4 (0.7) was observed after 2 years (mean and SD for each treatment are not presented in the article). In the GHLiquid-1516 trial (Japanese subjects with short stature born small for gestational age), mean difference of height SDS between 0.033 mg/kg/day and 0.067 mg/kg/day was 0.6 at 104 weeks. The results of the sample size calculations with power 80% can be seen in [Table 17-1](#) for different SDs and mean treatment differences that can be detected.

Table 17-1 Sample size per treatment group with power 80%

		Mean difference of 0.033 mg/kg/day and 0.066 mg/kg/day					
SD	0.35	0.40	0.45	0.50	0.55	0.60	
0.40	22	17	14	12	10	9	
0.45	27	21	17	14	12	10	
0.50	34	26	21	17	15	12	
0.55	40	31	25	21	17	15	
0.60	48	37	29	24	20	17	

With mean difference $\mu_2 - \mu_1 = 0.45$ and $SD = 0.5$, 21 subjects per treatment group give power 80%. In the GHLiquid-1516 trial, withdrawal rates were 6.1% and 5.9% for 0.033 mg/kg/day and 0.067 mg/kg/day, respectively. Assuming 10% of withdrawal rate from this result, sample size was determined as 24 per treatment group in order to ensure the power on PP analysis set. Thus, the sample size of 48 subjects in total is set, assuming exclusion of 6 subjects from PP analysis set.

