17.3 Primary endpoint

The primary endpoint is change in height SDS from baseline to 104 weeks of treatment¹⁷.

Statistical analysis

Since the primary objective of this trial is to evaluate the growth promoting effect of NN-220, the following hypothesis will be statistically tested; $H_0: \mu_1 = \mu_2$ vs. $H_1: \mu_1 \neq \mu_2$, where μ_i is the population mean, $i = 1, 2$ represents 0.033 mg/kg/day and 0.066 mg/kg/day, respectively. Primary analysis for the primary endpoint will be performed based on the ANCOVA model with treatment as a fixed effect and baseline height SDS as a covariate.

Sensitivity analysis

The same analysis as for the primary endpoint will be repeated on the PP analysis set.

All height SDS measurements at scheduled time points after randomisation will be analysed in a linear mixed model with treatment, time and interaction between treatment and time as fixed effects, baseline height SDS and interaction between baseline and time as a covariate and subject as a

random effect. This approach assumes that data are missing at random according to the taxonomy defined by Rubin (1976)²⁷. Treatment differences at 104 weeks will be estimated using this model.

Any marked difference concerning treatment differences between the sensitivity results and the result from the primary endpoint will be commented upon in the CTR.

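### LOCF enters the primary height SDS analysis by default, at small cost unless withdrawal is dose-related; the planned mixed model cannot check it because its week-104 standard error is too small

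*SAP*

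**What the plan says.** - **Missing data.** SAP section 2 and Protocol section 17 carry the same general rule: endpoints other than OGTT, HbA1c "and bone age will be imputed using the last observation carried forward (LOCF) method".
- **Primary analysis.** Protocol 17.3: "Primary analysis for the primary endpoint will be performed based on the ANCOVA model", with treatment and baseline height SDS as terms. SAP 2.3 repeats this. Neither gives a separate missing-data rule. The analysis set is the FAS (all randomised children), evaluated by intention to treat.
- **Sensitivity analyses.** There is a per-protocol repeat, and a linear mixed model on all scheduled post-randomisation heights, assuming data missing at random (MAR). The mixed model has treatment, time, baseline and their interactions with time, and subject as a random effect. No other covariance and no degrees-of-freedom method are stated.
- **Withdrawn children.** Protocol 8.1.4.3: "the investigator must aim to undertake procedures similar to those for Visit 20 as soon as possible". No later heights are described.
- **Planning figures.** Protocol 17.1 cites a Swedish study in which the change in height SDS, both doses pooled, "was 0.8 (0.4) after 1 year and a further mean gain of 0.4 (0.7) was observed after 2 years"; it adds that "mean and SD for each treatment are not presented in the article". In an earlier Japanese trial in children born small for gestational age, "withdrawal rates were 6.1% and 5.9% for 0.033 mg/kg/day and 0.067 mg/kg/day, respectively". The plan then assumes 10% withdrawal and sets 48 children, "assuming exclusion of 6 subjects from PP analysis set". Protocol 6.1: "Number of subjects expected to complete the trial: 42".

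**The concern.** Height SDS is still rising in year 2 on the cited figures, so a value frozen at withdrawal is not a neutral stand-in for week 104. It lowers both arm means. If withdrawal is balanced and both arms follow the pooled pattern, it also pulls the dose difference toward zero. If withdrawal differs by dose, it shifts the difference even when the doses are equally effective. The SAP does not say what quantity the frozen value is meant to estimate.

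The plan's safeguard is the mixed model, and the obvious remedy would be to promote it. But change from baseline starts near zero and spreads with time, while a model whose only random effect is a subject intercept assumes the same variance at week 4 as at week 104. Its week-104 comparison would then look far more precise than it is. Agreement with such a model says little about LOCF, and a disagreement in significance could be produced by the model itself.

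**Working it through.** **1. The plan's own figure.** Two-sided 5% t-test, difference 0.45, SD 0.5, 80% power (Protocol 17.1): exact calculation gives n = 20.39, so 21 per arm (power 81.2%). Allowing for 10% withdrawal, 21/0.9 = 23.3, so 24. All 30 cells of Table 17-1 reproduce. With 24 per arm and nobody missing, power is 86.3%.

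**2. Expected effect of LOCF.**

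From the protocol: pooled gain 0.8 + 0.4 = 1.2, so the share reached by week 52 is f = 0.8/1.2 = 2/3; planned difference 0.45.

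Assumed: arm gains 1.2 ± 0.225, i.e. 0.975 and 1.425; gain linear within each year; withdrawal uniform over 104 weeks; withdrawal-visit height carried forward. The pattern by arm is not given, so f is varied from 0.5 to 0.8 separately by arm.

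Mean share of the gain carried = ½[f/2 + (1+f)/2] = (1+2f)/4, so the mean shortfall = (3−2f)/4 = 5/12 at f = 2/3. That is 0.975 × 5/12 = 0.406 (low dose) and 1.425 × 5/12 = 0.594 (high dose).

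Expected difference = 0.45 − p(high) × 0.594 + p(low) × 0.406:

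| Withdrawal low / high | Calculation | Result (range over f) |
|---|---|---|
| 6.1% / 5.9% (cited) | 0.45 − 0.0350 + 0.0248 | 0.440 (0.429–0.450) |
| 10% / 10% (planned) | 0.45 − 0.0594 + 0.0406 | 0.431 (0.413–0.449) |
| 12.5% / 12.5% (3 of 24 each) | 0.45 − 0.0742 + 0.0508 | 0.427 (0.404–0.449) |
| 5% / 15% | 0.45 − 0.0891 + 0.0203 | 0.381 (0.360–0.400) |
| 15% / 5% | 0.45 − 0.0297 + 0.0609 | 0.481 (0.466–0.498) |

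With no true difference (both arms gain 1.2, mean shortfall 1.2 × 5/12 = 0.5), the false difference is 0.5 × [p(low) − p(high)]: 0.001 at the cited rates, −0.05 at 5%/15%.

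**3. Power and type I error of the LOCF ANCOVA.** Simulation: 24 per arm, week-104 SD 0.5, three assumed covariances (one child factor with SD 0.4 at year 1 and 0.5 at year 2; SD proportional to time; variance proportional to time), 4,000 trials each. Power was 85–87% with no withdrawals, 81–82% at the cited rates, 78–80% with three withdrawals per arm, and 74% if all six of those fall in year 1. With six withdrawals falling at random at equal risk and no true difference, type I error was about 5% and mean bias about zero. A second simulation with random-slope data gave a type I error of 4.8% at equal 10% withdrawal and 9.9% at 5% low/20% high; its power at equal 10% withdrawal was 72%, so the power loss depends on the assumed growth.

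**4. The planned mixed model.** With complete data and treatment by visit, a random-intercept model uses the variance averaged over visits. Its week-104 SE is therefore too small by the factor √(mean visit variance / week-104 variance).

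- SE needed: 0.5 × √(2/24) = 0.144.
- Take SD 0.1 at week 4, 0.4 at week 52 (cited) and 0.5 at week 104 (planning value), linear between. Over weeks 4, 8, 12, 26, 39, 52, 65, 78, 91 and 104 the SDs are 0.100, 0.125, 0.150, 0.2375, 0.319, 0.400, 0.425, 0.450, 0.475 and 0.500. The mean variance is 0.1225, so the factor is √(0.1225/0.25) = 0.70 and the model SE about 0.10. Type I error = 2[1 − Φ(1.96 × 0.70)] = 17%.
- With SD proportional to time plus measurement error of 0.1, the factor is 0.59, the SE about 0.085 and the type I error 25%.
- If variance were constant, the factor would be 1 and the error 5%.

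Simulated type I error was 17–26% with complete data, 18–29% with three withdrawals per arm, and up to 31% when poor growers leave.

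**The case against.** **The LOCF effect is small where the documents give figures.** This stands. At 6.1%/5.9% the shift is 0.01 SDS and simulated power stays above the planned 80%. Under balanced withdrawal LOCF errs toward no difference. If poor growers leave (MAR), it gives 0.46–0.48 against a true 0.45.

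**Chance imbalance is not bias.** A reader might infer that, since equal risk splits six withdrawals 5:1 or 6:0 in about 19% of trials, LOCF corrupts the test. It does not: over all splits, type I error stays near 5%. The 11–12% found when all six withdrawals fall in one arm is conditional on a split with probability 1.1% each way. Real inflation needs dose-related withdrawal, and the documents give no evidence of that.

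**Six withdrawals by week 104 is not stated.** This also stands. The six are per-protocol exclusions, which include eligibility violations, and the 42 completers may refer to the whole trial. Six is used here only as an assumption.

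**Understatement depends on the target.** Agreed: it holds for the gain under continued treatment. If the target is height at week 104 whatever happened after stopping, a MAR model could credit leavers with too much. The SAP states intention to treat but no target, which is itself a gap.

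**The plan already has checks.** Partly. The per-protocol repeat still uses LOCF: a child with 52 weeks of treatment and a week-65 height qualifies, and that height is carried to week 104. The mixed model fails as shown in step 4. Random intercept is the plain reading of the text; if another structure was meant, the SAP must say so.

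**Conclusion.** The point holds in two parts of unequal weight.

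LOCF governs the primary analysis by default. For a continued-treatment target, the cost at the cited rates is about 2% of the effect (0.44 against 0.45). At three withdrawals per arm the expected difference is about 0.43 and simulated power 78–80%, against 85–87% with none. Under equal-risk withdrawal the test keeps its size, so the documents do not support calling the primary test invalid. A false difference arises only if withdrawal is dose-related.

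The planned mixed model is the larger error. As written it can neither check nor replace the primary analysis, because it understates the week-104 standard error by 30–40% under the covariances assumed here. Variance growth from near zero at baseline follows from the endpoint being a change score; its exact path is assumed. The year-1 SD comes from a dose-pooled study and the week-104 SD from the planning table, so the 17–30% is a range under those assumptions, not a forecast. Confidence is medium.

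**What to change.** Before the first database lock, after which Protocol 11.2 opens the codes to the sponsor, list in SAP section 3:

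1. **State the estimand as an explicit choice.** If it is the week-104 dose difference under continued treatment, make primary a REML mixed model on observed height SDS in the FAS. Use treatment by visit, baseline by visit, Kenward-Roger degrees of freedom, and an unstructured covariance over weeks 26, 52, 78 and 104 (10 parameters, against 55 for all ten visits). Pre-specify a fallback such as random intercept and slope, noting that it can be conservative (simulated type I error 2–7%). Give a rule mapping the withdrawal-visit height to a scheduled visit, so that early leavers contribute.
2. **Keep the LOCF ANCOVA** as a sensitivity analysis.
3. **Whatever is primary, replace the random-intercept-only covariance** of the planned mixed model with the same structure and degrees-of-freedom rule.
4. **Add a tipping-point analysis** for departures from MAR, for example lowering withdrawn children's predicted week-104 values by 0 to 0.6 SDS, separately by arm. This range covers the average LOCF shortfalls of 0.41 and 0.59.

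Cost: no added children or visits. With no withdrawals the proposed model gave the same estimate, SE (0.145) and degrees of freedom (45) as the planned ANCOVA. With three withdrawals per arm it gave 0.45, power of 82–84% and type I error of 4–6%. Against that, it is a formal change of the primary analysis, it relies on MAR, it uses four of the ten post-baseline visits, and a child who leaves before week 26 adds nothing unless the mapping rule is in place.
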